of prostate cancer metastases and integrative copy number and gene expression analyses have identified mutations specific to specific metastases [7, 8]. Other authors have also identified important differences between primary and metastatic lesions including components of the AR pathways such as NCOA2 [9] and the polycomb complex chromatin suppressor EZH2 [10].

Furthermore, we have determined in RT-PCR analysis of primary and recurrent prostate carcinoma and distant metastases that the amino acid transport (AAT) proteins PAT1, LAT2 and ASCT2 as well as LAT1, xCT, LAT3 and ASCT1 are associated with malignancy. In analysis of lymph node metastases only, LAT1 and ASCT1 drop below significance. In addition, out of the AATs which were associated with malignancy, PAT1 had the highest correlation co-efficient of significance of expression to *anti*-3-[¹⁸F]FACBC uptake [38].

A. Specific Aims

Aim 1. Investigate the ability of *anti*-[¹⁸F]FACBC PET-CT and multiparametric/DW MRI imaging individually then together to detect local and extraprostatic recurrence of prostate cancer.

We will undertake a preliminary clinical trial with 25 patients post-definitive non-prostatectomy therapy for prostate carcinoma and who have suspected recurrence based on elevated PSA greater than nadir plus 2 ng/ml with absolute PSA \geq 4.0 ng/ml with any doubling time (DT) or with PSA 2.0-3.99 ng/ml with DT \leq 10 months. We will perform *anti*-[¹⁸F]FACBC PET-CT with early and delayed imaging, as well as multiparametric/DW MRI. Each study will be blindly interpreted then fused utilizing software registration and co-interpreted. Data from both studies will be used to direct biopsies to areas of concern in the prostate bed, and in extraprostatic locations. Results will be compared to the standard of pathologic analysis of prostate bed biopsies as well as clinical follow-up. The diagnostic performance of *anti*-[¹⁸F]FACBC PET-CT and multiparametric/DW MRI will be assessed individually then together. We will also determine if there is correlation between synthetic amino acid PET and MR, such as SUV and apparent diffusion co-efficient (ADC).

Rationale for AIM 1.

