As has been outlined in the Preliminary Results section of this proposal, *anti*-[¹⁸F]FACBC has been demonstrated to 1) have high sensitivity in the detection of recurrent prostate carcinoma though with suboptimal specificity in the prostate bed, and 2) the ability to differentiate prostatic from extraprostatic recurrence with high accuracy. *anti*-[¹⁸F]FACBC may thus have specific advantages for imaging recurrent prostate neoplasia within a clinical setting over conventional imaging. Yet, MR, especially with the addition of diffusion weighted imaging, has been reported in preliminary studies to provide high accuracy especially in the characterization of prostate bed recurrence. We hypothesize that utilization of a transmolecular approach combining synthetic amino acid radiotracer PET imaging with multiparametric MR has the potential to identify the presence and location of recurrent prostate carcinoma to a higher accuracy than either modality alone. **Therefore the most comprehensive manner to assess our hypothesis that PET-CT imaging with *anti*-[¹⁸F]FACBC in combination with multiparametric MR will lead to improved patient care resulting from detection of local and distant recurrent disease (Specific Aim #1) is to undertake a prospective clinical trial designed to address these issues.**

Secondary Aims

Aim 2. To determine mRNA differences between prostate carcinoma recurrent in the prostate bed and extraprostatic locations and to correlate any difference with quantifiable imaging biomarker data such as SUV for *anti*-[¹⁸F]FACBC PET-CT and ADC for MR.

Within the structure of the clinical trial (the same 25 patients) we will obtain sufficient tissue to perform mRNA sequencing on samples to exploit differences between the genetic profiles of recurrent prostate carcinoma in the prostate bed versus metastases. Since approximately 30% of patients with PSA > 4 ng/ml by our experience manifest with both prostate bed and nodal recurrence, we believe at least 8-10 patients in whom this comparison can be directly made will be available for analysis. This may also occur with lower PSA levels with faster DT. We will then correlate any differences in genotypic profile with imaging biomarkers from synthetic amino acid PET and MR, such as SUV and ADC.

Sub-aim 2a. To evaluate protein expression of previously identified amino acid transporters (AATs) that have been implicated in the uptake of *anti*-[¹⁸F]FACBC.

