We will undertake a **clinical trial with 25 patients** who have undergone definitive therapy for prostate carcinoma and who have suspected recurrence based on elevated PSA greater than nadir plus 2 ng/ml with absolute PSA \geq 4.0 ng/ml with any doubling time (DT) or with PSA 2.0-3.99 ng/ml with DT \leq 10 months. We will perform *anti*- ^{18}F FACBC PET-CT with early and delayed imaging as per the detailed protocol below. All patients will also undergo staging including multiparametric MR with diffusion weighted imaging. Other standard of care imaging such as bone scan, ProstaScint, CT, and transrectal ultrasound may also be performed per clinical judgment. These latter studies including MR are standard of care at our institution and will not be charged to the grant. We will investigate the ability of *anti*- ^{18}F FACBC PET-CT imaging to detect recurrence of prostate carcinoma in the prostate bed and in extraprostatic locations validated by pathologic analysis of prostate bed biopsies ideally guided by MR or ultrasound fusion of molecular to anatomic data in the prostate bed and percutaneous or laparoscopic guided biopsies of nodal and skeletal disease. Within the structure of the clinical trial, we will also evaluate the ability of transmolecular imaging with *anti*- ^{18}F FACBC PET-CT and multiparametric MR in the discrimination of prostatic from extra-prostatic recurrence, validated by a combination of pathologic analysis as well as imaging and clinical correlation. Though the grant itself extends for one year, patients may be followed up to 5 years to determine true negative imaging findings at minimal cost. Finally within the context of the clinical trial, tissue will be obtained for Aims 2 and Sub-aim 2a.

C1.1 Anti- ^{18}F FACBC radiolabeling

Methods. Production will be accomplished by the GE FastLab cassette system. Alternatively by automated synthesis developed by [name] and [name] [39] as outlined in Figure 15. The automated radiosynthesis of *anti*- ^{18}F FACBC will be carried out in a chemical process

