Receiver Operating Characteristic (ROC) analysis will be conducted to instigate the predictive power of FACBC PET and MR and determine if a variation in standard criteria or if combined criteria better maximizes sensitivity, specificity and accuracy of *each technique* using Chi-square test. The predictive accuracy of each technique will be determined using the positive predictive value (PPV) relative to the clinical and pathologic findings. The PPV of imaging will be assessed by calculating the probability of obtaining clinical and pathological outcomes that confirm the predicted positive findings based on the individual and combined scans. A similar negative predictive value (NPV) will also be calculated based upon a negative pathologic sampling as well as clinical/imaging follow-up at least 1 year or more. Formal hypothesis testing will be conducted to obtain inferences regarding differences between the predictive accuracies of these two approaches.

Each case will be evaluated as follows:

- 1) Results of biopsy as well as clinical follow-up will be correlated with prediction of local and distant neoplastic involvement by MR and *anti*-[¹⁸F]FACBC PET-CT.
- 2) Results of biopsy of lymph nodes or other extra-prostatic sites as well as clinical follow-up will be correlated with prediction of extraprostatic neoplasia by MR and *anti*-[¹⁸F]FACBC PET-CT.
- 3) Registered PET and MR will be correlated both qualitatively and quantitatively to pathologic and clinical results and in the discrimination of prostatic from extra-prostatic recurrence.
- 4) **Thus, truth for presence of disease will be established by biopsy/pathology and/or appropriate clinical followup. Truth for absence of disease will be established via pathologic sampling as well as standard clinical follow-up for at least 6 months and up to five years. We believe there will be enough patients with biopsy and clinically followed-up negative lymph nodes to calculate a true negativity rate.**

E2.0 Secondary Aims

Aim 2. and Sub-aim 2a.

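### Aim 1 compares reads made in the same men, but section E.1 names only an unqualified chi-square test and no paired method

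*Combined protocol and SAP*

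**What the plan says.** The main hypothesis (Rationale for AIM 1) is that combining PET with MR can "identify the presence and location of recurrent prostate carcinoma to a higher accuracy than either modality alone". Aim 1 describes a "preliminary clinical trial with 25 patients" and sets the order of reading: "Each study will be blindly interpreted then fused utilizing software registration and co-interpreted". Section C1.0 adds that "All patients will also undergo staging including multiparametric MR with diffusion weighted imaging". Section C1.6 builds the fused read from the same two scans after the individual reads, with one of the nuclear imagers and the primary MR imager reassessing the foci already recorded.

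Section E.1 is the only analysis plan for Aim 1. It contains:

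- ROC analysis, to "determine if a variation in standard criteria or if combined criteria better maximizes sensitivity, specificity and accuracy of" each technique, with the test given as "using Chi-square test. The predictive accuracy of each technique will be determined using the positive predictive value (PPV".
- PPV, assessed "based on the individual and combined scans", and a similar NPV.
- A closing promise: "Formal hypothesis testing will be conducted to obtain inferences regarding differences between the predictive accuracies of these two approaches". No test is named here, and the two approaches are not identified.

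No section names McNemar's test, a paired method for predictive values, a method for correlated ROC curves, or clustering of nodes within a patient.

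**The concern.** Whether the comparison is PET against MR, fused against PET, fused against MR, or one set of criteria against another, both results come from the same man. The evidence lies in the men on whom the two reads disagree: how many went from wrong to right, and how many from right to wrong. An independent-groups chi-square uses only the two totals correct. It therefore gives one p-value for a consistent gain and for a mixed one, and it uses the variance for two separate groups of men.

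The stake is the trial's main hypothesis. With so few men, the wrong variance can hide a real gain from fusion. If the test stays unnamed until the results are known, the choice of test can also change the conclusion.

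**Working it through.** **Inputs.** From the documents: 25 men (Aim 1); PET-CT, MR and the fused read in each man (Aim 1, C1.0, C1.6); in the PSA table under the Rationale for Aim 2, 41 + 25 = 66 of 73 men with PSA of at least 4 positive in the prostate bed. Aim 1 has no stated accuracy, effect size, correlation or power, so there is no plan figure to reproduce; the only power statement concerns the mRNA comparison. The accuracies and correlations below are assumptions, shown over a range. All tests are two-sided at 0.05.

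**Step 1: the variance.** For accuracies p1 and p2 with within-man correlation ρ,

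Var(difference) = [p1(1−p1) + p2(1−p2) − 2ρ√(p1(1−p1)p2(1−p2))] / n.

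The ordinary chi-square sets ρ = 0. With p1 = p2 = 0.70 and n = 25:

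- ρ = 0: 0.42/25 = 0.0168, SE 0.130
- ρ = 0.4: 0.42 × 0.6/25 = 0.0101, SE 0.100
- ρ = 0.6: 0.42 × 0.4/25 = 0.0067, SE 0.082
- ρ = −0.2: 0.42 × 1.2/25 = 0.0202, SE 0.142

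The chi-square SE is too large when ρ is positive and too small when it is negative.

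**Step 2: rejection rates.** These come from full enumeration of the paired 2×2 table, with P(both right) = p1p2 + ρ√(p1(1−p1)p2(1−p2)). Pearson chi-square has no continuity correction. With b gains, c losses and X ~ Binomial(b + c, ½), exact McNemar p = 2P(X ≤ min(b,c)), capped at 1; mid-p subtracts P(X = min(b,c)).

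No true difference, both accuracies 0.70, n = 25:

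| ρ | Chi-square | Exact McNemar | Mid-p McNemar |
|---|---|---|---|
| −0.2 | 7.7% | 2.5% | 4.4% |
| 0 | 5.4% | 2.3% | 4.2% |
| 0.2 | 3.2% | 2.0% | 4.0% |
| 0.4 | 1.4% | 1.4% | 3.3% |
| 0.6 | 0.3% | 0.6% | 1.9% |

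True accuracies 0.60 and 0.80, n = 25 (power):

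| ρ | Chi-square | Exact McNemar | Mid-p McNemar |
|---|---|---|---|
| 0 | 35% | 22% | 30% |
| 0.2 | 34% | 26% | 36% |
| 0.4 | 31% | 32% | 45% |
| 0.6 | 27% | 38% | 57% |

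**Step 3: one set of totals, three pairings.** Suppose a single read is right in 15 of 25 men and the fused read in 20. Pooled accuracy is 35/50 = 0.70, so chi-square = 0.20² / (2 × 0.70 × 0.30/25) = 0.04/0.0168 = 2.38, p = 0.12, whatever the pairing.

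| Gains, losses | Mid-p | Exact | Paired 95% CI for the 20-point gain (Newcombe) |
|---|---|---|---|
| 5, 0 | 0.031 | 0.0625 | 2 to 37 points |
| 6, 1 | 0.070 | 0.125 | −1 to 39 points |
| 8, 3 | 0.146 | 0.227 | −5 to 42 points |

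**Step 4: where testing is not useful.** Expected bed-positive men: 25 × 66/73 = 22.6, leaving 2.4 bed-negative. Mid-p McNemar cannot reach 0.05 with fewer than five discordant men (four gains and no losses give 0.0625). Bed specificity therefore cannot usefully be tested.

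**The case against.** **Chi-square is not clearly assigned to the main comparison.** Its sentence concerns varied or combined criteria for each technique, and the later formal comparison names no test. McNemar's test is itself a chi-square test, and ROC analysis is named too. This stands: a reader might infer that the plan prescribes a wrong test for fused against single reads, and the text does not go that far. But comparisons of criteria are also within-man, and nothing says that a paired form is meant.

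**The two approaches may be PET and MR.** E.1 opens with that pair and returns to it in its numbered items, while the PPV sentence speaks of individual and combined scans. The ambiguity is real. The plan should settle it; this review should not.

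**False positives are unlikely for the fused read.** This stands. A reader might infer inflated error from the 7.7%, but that needs negative correlation. The fused read reuses the same scans, earlier findings and some of the same readers, so positive correlation is expected. Rates above 5% are conceivable only for PET against MR.

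**The benefit depends on the version of McNemar chosen.** Also true. In the three pairings above, exact McNemar is non-significant each time, as chi-square is. In the power table it trails chi-square at correlations 0 and 0.2. This is a reason to name mid-p in advance.

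**Positivity for MR and the fused read is largely defined.** A reader might infer that no cutoff exists. C1.5 and C1.6 label scores 4 and 5 positive and 1 and 2 negative; only the indeterminate score, 3, is unassigned.

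**Conclusion.** The concern holds as under-specification that needs a named method. Every comparison in E.1 is within-man, so an independent-groups chi-square would be wrong whichever pair is meant.

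Under the assumed accuracies, at correlations of 0.4 to 0.6, its type I error falls to between 1.4% and 0.3%, and its power is about 14 to 30 percentage points below mid-p McNemar (31% against 45%; 27% against 57%). The expected harm is a missed gain. The rates depend on assumed accuracies and correlations and take 25 evaluable men as the best case; C1.7 allows numbers to differ between sub-analyses.

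It is not a fatal flaw. The trial calls itself preliminary, and the paired counts can still be recovered at analysis. Nor does the change guarantee more power; the case for it is validity and a test fixed in advance.

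**What to change.** In E.1:

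- Replace the chi-square test with mid-p McNemar on per-patient accuracy and sensitivity, and on specificity for extraprostatic disease only.
- Say which pairs the formal comparison covers: PET against MR, fused against PET, fused against MR.
- Report gains, losses and a paired 95% confidence interval for each difference.
- Compare PPV and NPV with a paired method (generalised score test or patient-level bootstrap), because their denominators differ between reads.
- Cluster any node-level test by patient.
- State, before unblinding to truth, how score 3 is counted.
- Report prostate-bed specificity and NPV descriptively only, since about 2 to 3 bed-negative men are expected.

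The cost is SAP wording and a little more analysis; no new patients, scans or readers. The downside is that near zero correlation, or in small groups, the paired test can have less power than chi-square (30% against 35% at correlation 0). With 25 men and several comparisons, all results should be labelled exploratory.

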One PET radiotracer which has shown promise in the staging and restaging of patients with prostate carcinoma is *anti*-1-amino-3-[¹⁸F]fluorocyclobutane-1-carboxylic acid (*anti*-3-[¹⁸F]FACBC) which is a synthetic amino acid analog with little renal excretion and transport via sodium dependent and independent pathways [33-35]. In a recent study, *anti*-3-[¹⁸F]FACBC demonstrated higher accuracy compared with ¹¹¹Indium-capromab-pendetide in the restaging of patients with suspected recurrent prostate carcinoma [36]. Yet there was suboptimal specificity in the prostate bed, especially after non-radical prostatectomy therapy. It is not yet clear if this was the result of sampling error during biopsy and/or nonspecific uptake by *anti*-3-[¹⁸F]FACBC in non-neoplastic tissue.

In one study of patients with both primary and recurrent prostate carcinoma, DWMR demonstrated significant differences of mean apparent diffusion coefficients (ADC) between malignant and benign nodes with an accuracy of 85.6% (sensitivity 86%, specificity 85.3%) compared with an MR accuracy of 66.1% based on nodal size alone. Yet there was significant overlap of individual ADC values between benign and malignant foci [18]. In addition, less than 50% of patients had histologic follow-up and 6 month follow-up was accepted as truth in those without histologic confirmation. In another recent study in patients with suspicion of recurrence after high dose brachytherapy, DWMR was noted to have a sensitivity of 68% and a specificity of 95% in the detection of tumor in the prostate bed [37]. Multiparametric MRI achieved the highest sensitivity (77%) but with slightly decreased specificity (92%).

Thus, there may be utility in combining both multiparametric MR and synthetic amino acid PET as a hybrid transmolecular technique in the detection and restaging of recurrent prostate carcinoma. The data from this study could be used to design a more comprehensive study that would lend itself to novel PET-MR hybrid devices which are now commercially available.

There may also be genotypic and phenotypic differences between prostate carcinoma recurrence in the prostate bed and in extraprostatic nodal locations. Exome sequence analyses

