Depending on the normality of data distribution, t-test or Wilcoxon rank sum test will be conducted to compare the mRNA differences, genomic differences in gene expression, alternative splicing, indels and single base mutations between prostate carcinoma recurrent in the prostate bed and extraprostatic samples. Analysis of variance (ANOVA) will be used to compare the IHC staining of protein levels between the different categories of FACBC uptake. Tukey pairwise comparison will be further conducted when the overall comparison with ANOVA

Version 9-23-13

Version 11-6-13

Version 11-11-14

Version 12-4-14

is significant at the significance level of 0.05. Pearson/Spearman correlation coefficients will be estimated to measure the associations: 1) between mRNA levels of candidate AAT genes and FACBC uptake; 2) between mRNA differences and quantifiable imaging biomarker data such as SUV for *anti*-[¹⁸F]FACBC PET-CT and ADC for MR. Multivariate analyses will further be conducted, in which general linear model (GLM) will be employed to assess the adjusted relationships mentioned above after adjusting for the other covariates.

Sample size and power calculation

The sample size of this study is 25 patients. The power calculation is based on the comparison of mRNA differences between the prostate bed and extraprostatic samples using two sided t-test. At the significance level of 0.05, the sample size of 25 will achieve a power of at least 80% to detect one standard deviation or higher difference in mRNA difference between the two groups of samples.

F. Adverse Event Reporting

An adverse event is defined as any untoward medical occurrence associated with the use of a drug in humans whether or not considered drug-related

A significant shift from baseline which can be attributable to the radiotracer injection and not the patient's medical condition will be considered an unexpected AE. An event greater than 7 days post scan will not be considered an AE since 95% of ligand is eliminated by 7days.

The National Cancer Institute's Common Terminology Criteria for Adverse Events (CTCAE) Version 4.03 (June 14, 2010) will be used as a guide address potential AEs subject to limitations above and medical and scientific judgment as to plausibility of such criteria in a diagnostic radiotracer study.

Adverse Event Reporting

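### Read literally, Aim 1's formal test compares PPV, which leaves out missed disease, while the stated hypothesis is that combined PET-MR is more accurate than either scan alone

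*Combined protocol and SAP*

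**What the plan says.** The rationale for Aim 1 hypothesises that combining the two scans can "identify the presence and location of recurrent prostate carcinoma to a higher accuracy than either modality alone".

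Section E.1 covers the analysis in three steps.

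- An ROC analysis with a chi-square test asks whether varied or combined criteria improve the sensitivity, specificity and accuracy of each technique.
- Predictive accuracy is then defined: "The predictive accuracy of each technique will be determined using the positive predictive value (PPV) relative to the clinical and pathologic findings". A similar NPV is also to be calculated.
- Formal hypothesis testing follows, to obtain "inferences regarding differences between the predictive accuracies of these two approaches".

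E.1 does not say which two approaches are meant. For this comparison it names no test, significance level or paired method.

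**The concern.** The hypothesis and the test concern different quantities. Accuracy counts every wrong call, including recurrences a scan misses. PPV is the share of positive calls that are true, so a missed recurrence never enters it. A scan can find much more disease and show no gain in PPV, and a stricter scan can rank higher on PPV while missing more.

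The contrast is also unclear. Two approaches most naturally means PET against MR, whereas the hypothesis sets the combined reading against each scan alone.

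At stake is whether the one formal comparison promised for Aim 1 answers the Aim 1 question. If the tested measure stays open, it could also be chosen after the results are known.

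**Working it through.** **1. The plan's own power figure.** The only power statement is under Sample size and power calculation. It concerns mRNA: at least 80% power "to detect one standard deviation or higher difference in mRNA difference between the two groups of samples". With a two-sided t-test at 0.05, 25 samples per site give 93.4% and 25 pairs give 99.8%, so the figure holds as a lower bound if all 25 men contribute at both sites. It says nothing about Aim 1, for which no power is stated.

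**2. Inputs.**
- 25 men, about 23 with bed disease and about 9 with nodal disease (Rationale for Aim 2 and Sub-aim 2a). This leaves 25 − 23 = 2 bed-negative and 25 − 9 = 16 extraprostatic-negative men.
- Diffusion-weighted MR 68%/95% and multiparametric MRI 77%/92% (Background and Significance). These come from a prostate-bed study, so using them for the extraprostatic region is an assumption.
- All other accuracies, the between-scan correlation of 0.5 and the two-sided 0.05 level for Aim 1 are assumptions.

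**3. PPV and accuracy move in opposite directions.** With sensitivity Se, specificity Sp and prevalence p:

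PPV = Se·p / [Se·p + (1 − Sp)(1 − p)]; accuracy = Se·p + Sp(1 − p).

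| Region | Reading | PPV | Accuracy |
|---|---|---|---|
| Bed, p = 0.92 | 68%/95% | 0.6256/0.6296 = 0.994 | 0.6256 + 0.0760 = 0.702 |
| Bed | 77%/92% | 0.7084/0.7148 = 0.991 | 0.7084 + 0.0736 = 0.782 |
| Extraprostatic, p = 0.36 | 68%/95% | 0.2448/0.2768 = 0.884 | 0.2448 + 0.6080 = 0.853 |
| Extraprostatic | 77%/92% | 0.2772/0.3284 = 0.844 | 0.2772 + 0.5888 = 0.866 |

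The more accurate reading has the lower PPV in both regions.

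**4. The PPV null can be exactly true when accuracy differs widely.** At a given prevalence PPV depends only on Se/(1 − Sp). Take assumed values of 90%/80% and 45%/90%: 0.90/0.20 = 4.5 and 0.45/0.10 = 4.5. At the bed prevalence in the protocol's PSA table (66/73), both PPVs are 97.7%, while accuracy is 89% against 49%.

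**5. Power by simulation.** n = 25, two-sided 0.05, latent correlation 0.5. PPV and NPV use a paired weighted score test, which is approximate in cells this small. Sensitivity uses exact McNemar in truth-positive men. Ranges show the spread between separate runs.

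| Setting | PPV | NPV | Sensitivity |
|---|---|---|---|
| Bed, Se 60% vs 95%, Sp 80% both | 12–13% | 79–80% | 82–83% |
| Bed, same Se, Sp 50% both | 34% | 58% | 81–83% |
| Extraprostatic, Se 30% vs 95%, Sp 90% both | 26–28% | 88–89% | 60–61% |

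In the extraprostatic region at 50%/95% against 90%/85%, McNemar on sensitivity has only 11–12% power. The observed PPV favours the less sensitive scan in 64–65% of trials, but significantly so in only 0.7%.

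**6. What McNemar can do with these counts.** The smallest two-sided exact p with k discordant men, all in one direction, is 2 × 0.5^k.
- k = 2 gives 0.5, so a bed specificity test on 2 negative men can never reject.
- k = 5 gives 0.0625 and k = 6 gives 0.031, so at least 6 one-way discordant men are needed.

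**The case against.** **NPV may be part of the test.** The testing sentence follows both PPV and NPV, so a fair reader could take predictive accuracies to cover both. NPV responds to missed disease, with power of 58% to 89% in the step 5 settings. This stands: a reader might infer that Aim 1's test is blind to missed disease and nearly powerless, and the documents do not support that. They define predictive accuracy by PPV and only calculate NPV, but they do not exclude NPV from testing. The defect is an ambiguity with one poor literal reading.

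**Sensitivity, specificity and accuracy are already analysed.** The ROC sentence covers them and mentions combined criteria, so missed disease is not invisible to Aim 1. But that sentence concerns the choice of criteria. It is not the one that plans the formal comparison.

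**The low PPV power is conditional.** The large sensitivity gaps are assumed. On the protocol's own MR figures both tests fail: PPV 0.3% and McNemar 5% in the bed, 0.5% and 0.2% extraprostatically. When nodal specificities differ strongly, a PPV test can have real power: 50–76% at 90%/40% against 68%/95% with independent readings. It then favours the less sensitive scan, which in that setting is also the more accurate one (0.854 against 0.578).

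**PPV is easier to verify.** C1.7 says nodes are not biopsied when all imaging is negative, so sensitivity leans on follow-up. This stands as a limitation of the fix. The plan nonetheless already intends to establish absence of disease by sampling and follow-up.

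**The trial is preliminary.** True, but E.1 still promises formal testing, so the tested quantity should match the hypothesis.

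**Conclusion.** The concern holds in a limited form. On its literal reading E.1 formally tests PPV between two unnamed approaches, while the hypothesis is that combined imaging is more accurate than either modality alone. These are different nulls, whatever accuracies are assumed. The reversal in step 3 needs only the protocol's figures, with the bed-study values carried over for the extraprostatic region.

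The size of the power loss depends on assumptions. In the bed, at 23 of 25 diseased, a PPV test has about 12% power against about 83% for McNemar on sensitivity. That rests on sensitivities of 60% and 95%, specificity 80% for both and correlation 0.5. Low power for PPV should not be claimed as a general result, nor that a significant PPV result would often mislead. The change corrects what is tested. It does not make 25 men sufficient for the extraprostatic comparison.

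**What to change.** In E.1:

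- Name as the formal Aim 1 test an exact McNemar comparison of sensitivity in truth-positive men, separately for the bed and the extraprostatic region, for combined imaging against each modality alone. State the significance level.
- Use a positivity cut-off fixed in advance. C1.4 gives one for PET. C1.5 and C1.6 record a five-point confidence score without saying which scores count as positive, so add that.
- Compare specificity formally only in the extraprostatic region (about 16 negatives). Report bed specificity descriptively with an exact interval, because about 2 negatives cannot give a significant result.
- Report PPV and NPV with confidence intervals and the observed prevalence, and base no superiority claim on PPV alone.

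The cost is wording only: the same reads and truth data serve. PPV loses its p-value. Extraprostatic tests stay weak with about 9 positive men (about 11% power at 50%/95% against 90%/85%). Sensitivity relies on follow-up rather than biopsy for image-negative nodes, which should be stated as a limitation.
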